3. DESCRIPTION OF RESEARCH PROTOCOL

A. Study Design – Overview, Methods, Procedures

Study Design

Forty consenting IBS-D patients and twenty consenting IBS-C patients will undergo a 7-day screening period beginning with the baseline visit. Patients fulfilling the inclusion and exclusion criteria will undergo a i) flexible sigmoidoscopy to obtain colonic mucosal samples from the recto-sigmoid junction for assessment of intestinal permeability, mucosal immune cell abundance, and mucosal microbiome ii) stool collection for microbiome analysis iii) serological markers of intestinal permeability and iv) saccharide excretion assay. They will then go on a 4-week low FODMAP diet followed by a repeat flexible sigmoidoscopy with biopsies, stool collection, serological markers of intestinal permeability and saccharide excretion assay.

Baseline Visit

- Informed consent will be obtained from the subjects
- Medical history including IBS history will be obtained from the subjects
- Blood samples will be obtained
- Subjects will be instructed on the online questionnaires (described below) to be completed for the duration of the study.
- Subjects will be given a stool collection kit for collection prior to their next visit. The stool will be collected from the subjects' home and brought with frozen icepacks to their next visit.
- Subjects will be given the lactulose-mannitol standard solution and be instructed on urine collection for the test. Subjects will drink the solution first thing in the morning on a day of his or her choice prior to the Initiation Visit and collect of all their urine in a jug for the next 24 hours.

Initiation Visit (7 days post-baseline visit +/- 7 day)

- Subjects will undergo a flexible sigmoidoscopy in MCRU. The flexible sigmoidoscopy will only be performed up to the rectum. Subjects are not required to prep for the procedure (e.g. no diet restrictions or laxatives). Sedation will not be given to the subjects.

- Twelve biopsies will be obtained from the recto-sigmoid junction.
- Subjects will be given the low FODMAP diet instructions. Subjects will be instructed to stay on the low FODMAP diet for 4 weeks.
- Subjects will be given the lactulose-mannitol standard solution and be instructed on urine collection for the test. Subjects will drink the solution first thing in the morning on a day of his or her choice in the week prior to the Post-Diet Visit and collect of all their urine in a jug for the next 24 hours.

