- Subjects will be given a stool collection kit for collection prior to their next visit. The stool will be collected at the subject's home in the week prior to the Post-Diet Visit and brought with frozen icepacks to the Post-Diet Visit.

Post-Diet Visit (28 days post-Initiation Visit +/- 5 days)

- Subjects will undergo a flexible sigmoidoscopy in the MCRU. The flexible sigmoidoscopy will only be performed up to the rectum. Subjects are not required to prep for the procedure (e.g. no diet restrictions or laxatives). Sedation will not be given to the subjects.
- Twelve biopsies will be obtained from the recto-sigmoid junction.
- Subjects will return the urine collection container.
- Blood samples will be obtained

Low FODMAP diet

Subjects who consent to participate in the study will be given low FODMAP meals delivered to their home by Epicured at no charge to the subject. Epicured is a meal delivery service that provides ready-to-eat low FODMAP meals. Subjects will be required to provide their home address and name to Epicured in order to receive the delivery 2-3x/week. Epicured will provide 3 meals, 2 snacks and 1 non-water beverage to subjects for each day of the 4 week low FODMAP period. Vegetarian, vegan, and omnivore meals will be provided. Subjects will be told to only ingest Epicured provided items (excluding water).

Healthy Control Arm

The stool of healthy subjects will be collected to compare to the IBS subjects' stool (details of analysis below). These subjects will be recruited from UMIHealthResearch.org. Their medical records will be used to ascertain eligibility and to collect demographic information. The study team will consent and give the subject a stool collection kit. The subjects will return the stool to the study team and their participation in the study will end at that time.

IBS-C Arm

Like IBS-D, the physiological effects of a low FODMAP diet are unclear in patients with IBS-C. The relationship between the physiology of IBS-C and IBS-D, if there any, is also unclear. Thus, as a disease comparison group, 20 patients with IBS-C will be enrolled in the study in order to better understand how a low FODMAP diet effects and changes the microbiome and intestinal permeability of IBS-C patients.

In vivo Intestinal Permeability:

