Two colonic mucosal biopsies and stool samples obtained before and after the dietary intervention would be used for this analysis. Once obtained, each biopsy will be washed using Sterile PBS to remove non-adherent luminal/fecal material. The biopsy samples will be weighed, flash frozen in liquid nitrogen and stored at -80C for DNA extraction and microbiological analysis. DNA extraction will be done using a QIAamp DNA Mini Kit (Qiagen, Crawley, UK) per manufacturer's instructions. Bacterial community composition in isolate DNA samples will be characterized by amplification of the V1-V3 variable regions of the 16sRNA gene by polymerase chain reaction for both mucosal and fecal samples. 16S rRNA PCR products will be quantified, pooled and purified for the sequencing reaction. 454 GS FLX Titanium sequencing will be performed on a 454 Life Science Genome Sequencer FLX machine for both mucosal and fecal samples. Sequencing data generated will be processed by the Quantitative Insights into Microbial Ecology Pipeline (QIIME). Sequences will be screened for chimeras using the ChimeraSlayer algorithm, and all potential chimeras will be excluded from downstream analysis. Sequences less than 200 bp or greater than 1000 bp in length, those with average quality scores <20, incorrect primer sequences, or more than 1 ambiguous base will be excluded from downstream analysis. The quality filtered sequences will be assigned to operational taxonomic units (OTUs; sequences that share \geq 97% similarity) using a closed reference approach in QIIME with the UCLUST algorithm and the Greengenes reference database. According to the results of OTUs analysis, a diversity analysis including Simpson, Shannon, Chao 1, ACE and Good's Coverage will be carried out by QIIME. β diversity metrics, including (UniFrac weighed or unweighted) will also be calculated.

Stool samples will also be obtained from 30 healthy controls aged 18-65 years without any known gastrointestinal history and who do not report any abnormal bowel movements or abdominal pain. Stool samples from healthy controls will be utilized for analyzing fecal microbiome using the methodology described above. Their microbiome will be compared with microbiome of IBS-D patients pre and post LFD.

Clinical variables

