B. Statistical Considerations

Sample Size Justification: Statistical analysis

All continuous variables will be tested for normality using the Shapiro-Wilk test. Normally distributed continuous data will be presented as mean (\pm SD) and will be compared pre-and post-dietary interventions using paired Student's t-test. Continuous data which are not normally distributed will be presented as median (range) and compared using Wilcoxon signed-rank test. Proportions will be expressed as percentages and compared using chi-square test or fisher exact test as appropriate. Since we anticipate that most of our tests will involve continuous data that is normally distributed, we based our power analysis on pre-post comparisons using paired t-tests. Assuming two-tailed tests, with alpha set at 5%, a sample size of 20 will provide 80% power to detect a medium effect size (i.e., Cohen's d=.5) when the pre-post correlation is r=.7.

C. Subject Selection

Inclusion criteria for IBS subjects

Patients with IBS-D or IBS-C diagnosed per Rome IV questionnaire and without any alarm features (rectal bleeding, weight loss, nocturnal symptoms, family history of inflammatory bowel disease or celiac disease) will be considered for the study if they had:

- i) Aged 18-65 years at the time of screening
- ii) Normal serum studies including serum tissue-transglutaminase antibodies, thyroid stimulating hormone levels, C-reactive protein, complete blood count since the onset of symptoms
- iii) Normal stool studies including, ova and parasites since the onset of symptoms
- iv) IBS-SSS score of ≥ 175 at the end of the 7-day screening period

In case of presence of any alarm features and/or elevated inflammatory markers (C-reactive protein or fecal calprotectin), patients will be eligible if they have been excluded for inflammatory bowel disease with upper endoscopy, and colonoscopy in the last one year.

Exclusion criteria for IBS subjects

- i) individuals already on a LFD or other dietary restriction such as gluten free diet within the past 6 months
- ii) individuals with any known food allergy or insulin-dependent diabetes
- iii) known history of celiac disease, inflammatory bowel disease or microscopic colitis
- iv) prior small bowel or colonic surgery or cholecystectomy
- v) pregnant patients
- vi) Antibiotics in the past 3 months

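### No minimum gap is set between a bowel-prepared colonoscopy and the baseline microbiome samples, so recovery from preparation could be counted as, or hide, a diet effect

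*Combined protocol and SAP*

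**What the plan says.** Section 3.C attaches a colonoscopy condition to one subgroup of IBS patients, those with alarm features or a raised C-reactive protein or calprotectin. The rule for them is: "patients will be eligible if they have been excluded for inflammatory bowel disease with upper endoscopy, and colonoscopy in the last one year". No lower limit on the interval appears there or elsewhere.

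The IBS exclusions in the same section contain one washout aimed at a recent disturbance of the flora: "vi) Antibiotics in the past 3 months". They do not mention bowel preparation, purgatives or recent colonoscopy. Healthy volunteers have the same antibiotic rule and also a 3-month gastroenteritis rule, which IBS patients do not have.

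Section 3.A says of both study sigmoidoscopies: "Subjects are not required to prep for the procedure (e.g. no diet restrictions or laxatives"). This covers the study procedures only, not an earlier diagnostic colonoscopy.

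The schedule in Section 3.A fixes the sampling times:
- First biopsies: "Initiation Visit (7 days post-baseline visit +/- 7 day").
- Baseline stool: "Subjects will be given a stool collection kit for collection prior to their next visit", so between the Baseline and Initiation Visits.
- Second biopsies: "Post-Diet Visit (28 days post-Initiation Visit +/- 5 days").

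The microbiome part of Section 3.A states: "Two colonic mucosal biopsies and stool samples obtained before and after the dietary intervention would be used for this analysis". Section 3.B compares continuous measures before and after the diet with a paired t-test or a signed-rank test. Every IBS patient receives the diet.

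**The concern.** The plan keeps its own sampling free of bowel preparation and screens out recent antibiotics, so it recognises that the baseline flora should be undisturbed. It leaves open a route by which a baseline could be disturbed anyway, and for one subgroup it makes the procedure concerned a condition of entry.

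If the flora of such a patient is still recovering at baseline and has recovered by the post-diet samples, the within-patient change contains recovery as well as diet. The design cannot separate the two. There is no concurrent IBS group without the diet, and healthy controls give a single stool sample and then leave the study.

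The error can go either way. Recovery in a diversity index or taxon could be reported as a rise due to diet, or it could offset a genuine fall. The second matters because Section 2 cites a human study in which the diet lowered butyrate-producing bacteria. The mucosal and fecal microbiome is one of the three stated aims, and the hypothesis in Section 1 starts from a change in it.

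**Working it through.** **1. Shortest gap the text allows.** The Initiation Visit is 7 ± 7 days after Baseline, so first biopsies and baseline stool fall 0 to 14 days after Baseline. With no minimum before Baseline, the shortest permitted gap from colonoscopy to baseline sampling is effectively 0 days. Screening itself imposes at most 14. The second biopsies follow 28 ± 5 days later, at 23 to 33 days.

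**2. The plan's own power figure.** Section 3.B gives n=20, d=.5, r=.7, two-sided 5%, power 80%. The standardised paired effect is dz = 0.5/√(2(1−0.7)) = 0.645. The noncentral t gives 78.2% power at n=20, and 80% needs n=21. The stated figure is reproduced to within 2 points and is not in dispute. At the planned 40 IBS-D patients, the same inputs give 97.8%.

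**3. Model for the disturbance.** From the plan: n=40, r=.7, two-sided 5%. The SD of the change is √(2(1−0.7)) = √0.6 = 0.775 baseline SDs.

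Assumed, not in the documents: k patients have a baseline that is s SD too low and has recovered by the post-diet visit, with k = 1, 2 or 4 and s = 0.5, 1.0 or 1.5. The mean change is then shifted by ks/40, from 1×0.5/40 = 0.0125 SD to 4×1.5/40 = 0.15 SD. The largest shift is 30% of d=.5.

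**4. Simulated paired t-test, n=40.** Whole percentages; repeat runs differ by up to about a point.

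| k | s (SD) | False-positive rate, no diet effect | Power, 0.5 SD fall | Power, 0.35 SD fall |
|---|---|---|---|---|
| 0 | – | 5 | 98 | 79.5 |
| 1 | 0.5 | 5 | 97 | 76 |
| 1 | 1.0 | 5 | 96 | 72 |
| 1 | 1.5 | 5 | 95 | 67 |
| 2 | 0.5 | 5 | 96 | 73 |
| 2 | 1.0 | 6 | 94 | 64 |
| 2 | 1.5 | 7 | 89 | 52 |
| 4 | 0.5 | 6 | 94 | 65 |
| 4 | 1.0 | 10 | 86 | 46 |
| 4 | 1.5 | 14 | 69 | 25 |

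The 0.35 SD fall is not in the plan. It is the effect that clean data at n=40 detect with about 80% power.

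**5. Hand check of the worst row (k=4, s=1.5).** A mixture of shifted and unshifted patients also widens the observed SD of change: √(0.6 + 0.1×0.9×1.5²) = √0.8025 = 0.896. The estimated standard error is 0.896/√40 = 0.142, so the mean change must exceed about 2.02×0.142 = 0.287 in size. The true sampling SD of the mean is 0.775/√40 = 0.1225.
- No diet effect, mean change 0.15: (0.287−0.15)/0.1225 = 1.12, tail about 13%.
- 0.5 SD fall, mean change −0.35: (0.35−0.287)/0.1225 = 0.51, power about 70%.
- 0.35 SD fall, mean change −0.20: (0.20−0.287)/0.1225 = −0.71, power about 24%.

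These agree with the simulation to about a point.

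**The case against.** **The premise is not in the documents.** They do not say that the diagnostic colonoscopy used a preparation, or what preparation does to the flora, by how much or for how long. This stands as a limit on magnitude: preparation is the ordinary assumption, and the size of any bias cannot be derived from the plan. It does not close the gap in the eligibility rules.

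**Few patients may be exposed.** The default entrant has no alarm features and a normal C-reactive protein; colonoscopy is required only in the exception, whose share is not given. Suppose 10 to 30% of 40 patients had a colonoscopy, spread evenly over 52 weeks, with disturbance lasting 2 to 4 weeks. The expected number disturbed at baseline is 40×0.10×2/52 = 0.15 to 40×0.30×4/52 = 0.9. The binomial chance of 2 or more is 1 to 24%, and of 4 or more at most 1.3%. These figures are also assumptions, and work-up clustered just before referral would raise them. The objection stands in part: the rows with 4 patients are an upper illustration, not an expectation.

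**A reader might infer that power collapses.** The drop to 25% needs 4 affected patients, a 1.5 SD shift and an effect smaller than the plan's. At d=.5 the same contamination leaves 69%, and 2 patients leave 89% or more.

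**A reader might also infer that a 3-month washout is required, or that healthy controls share the defect.** The 3 months belong to the antibiotic rule, and nothing shows that the two disturbances last equally long. Controls give one stool sample, need no colonoscopy and are excluded for a history of gastrointestinal illness. Recovery cannot be mistaken for a diet effect in them; only the cross-sectional comparison could be touched.

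**Conclusion.** The gap is real and the point holds as a low-cost improvement. The plan sets a maximum but no minimum interval for a colonoscopy that some IBS patients must have had, gives bowel preparation no washout, and analyses change without a concurrent control.

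The size depends wholly on assumed inputs. With 1 or 2 affected patients the false-positive rate stays at about 5 to 7%, and power for d=.5 stays at 89% or above; power for a 0.35 SD fall can still drop to 52% in the harshest of these cases. With 4 affected patients the false-positive rate is 6 to 14% and power for d=.5 is 94 to 69%. Masking of a modest real fall is therefore the larger risk. The documents do not show that any bias will occur, and the figures apply to the microbiome measures only.

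**What to change.** Add one line to the IBS eligibility criteria in Section 3.C: a minimum interval between any bowel preparation, for whatever reason, and the baseline stool and mucosal microbiome samples. The investigators should set and justify its length; the plan's existing 3-month antibiotic washout is a convenient default. Defer the Baseline Visit of affected patients rather than lose them.

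Record the date of the last preparation for every IBS patient. If some recently prepared patients are already enrolled, repeat the microbiome pre-post analysis without them and report both results.

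For healthy volunteers the same line is optional, since it protects only the cross-sectional stool comparison.

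The cost is one eligibility line, one data field and the deferral of a few patients.

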- vii) Those who regularly use mast cell stabilizers or anti-histaminic or non-steroidal anti inflammatory agents (NSAIDs) excluding daily baby aspirin or steroids or bile-acid binder.

Inclusion criteria for healthy volunteers

Aged 18-65 years

Exclusion criteria for healthy volunteers

1. History of gastrointestinal illness
2. Self-reported constipation, diarrhea, or abdominal pain
3. Antibiotics in the past 3 months
4. Gastroenteritis in the past 3 months

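### Healthy controls are neither excluded nor assessed for restricted diet, insulin-dependent diabetes or regular medications that exclude IBS patients, so their stool comparison with IBS-D may be confounded

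*Combined protocol and SAP*

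**What the plan says.** Section 3.A (Mucosal and fecal microbiome) sets up the control group: "Stool samples will also be obtained from 30 healthy controls aged 18-65 years without any known gastrointestinal history". Its purpose is stated there too: "Their microbiome will be compared with microbiome of IBS-D patients pre and post LFD".

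Section 3.C requires healthy volunteers to be 18-65 and lists four exclusions: "History of gastrointestinal illness", "Self-reported constipation, diarrhea, or abdominal pain", "Antibiotics in the past 3 months" and "Gastroenteritis in the past 3 months".

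The IBS list in the same section is longer. It also removes "individuals already on a LFD or other dietary restriction such as gluten free diet within the past 6 months" (item i), "individuals with any known food allergy or insulin-dependent diabetes" (item ii), patients with earlier bowel surgery or gallbladder removal (item iv), pregnant patients (item v), and regular users of several drug classes (item vii). I read item vii as covering NSAIDs other than daily low-dose aspirin, steroids, bile-acid binders, antihistamines and mast-cell stabilizers.

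Section 3.A (Healthy Control Arm) has controls give one stool sample and then leave. Their medical records serve only to confirm eligibility and supply demographics. The food and drink record under Clinical variables is described for patients. Section 3.B covers pre-post tests and tests of proportions. It mentions no matching, covariate adjustment or sensitivity analysis for the control comparison.

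**The concern.** The control group is the reference for what healthy stool looks like. If controls may carry factors that were removed from the patients, a difference between the groups can reflect those factors as well as disease.

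Diet is the clearest case, because the protocol itself ties it to the microbiome. Section 1 hypothesizes that LFD changes the mucosal microbiome, and section 2 cites human data in which LFD lowered butyrate-producing bacteria. On that premise, a control already eating an LFD carries part of the intervention's effect into the reference group. The plan treats a recent restricted diet as disqualifying in patients and gives no reason for allowing it in controls.

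As written, the imbalance could be neither seen nor corrected at analysis. Diet and drug use are not eligibility items for controls, so the record check need not look for them, and no other step collects them. What is at stake is the interpretation of any statement that IBS-D stool differs from, or after LFD approaches, healthy stool.

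**Working it through.** **1. The lists side by side (section 3.C)**

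| Factor | IBS patients | Healthy controls |
|---|---|---|
| LFD, gluten-free or other restricted diet, 6 months | excluded | not excluded |
| Insulin-dependent diabetes | excluded | not excluded |
| Regular item vii drugs | excluded | not excluded |
| Food allergy, pregnancy | excluded | not excluded |
| Bowel surgery | excluded | not named; normally caught by the gastrointestinal-history wording |
| Cholecystectomy | excluded | not named; unclear |
| Antibiotics, 3 months | excluded | excluded |
| Gastroenteritis, 3 months | not named | excluded |

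Diet, diabetes and the item vii drugs are plain gaps, and cholecystectomy is a possible one. The antibiotic rule is identical in both groups.

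**2. The plan's own power figure.** Section 3.B states 80% power for a paired test with n = 20, d = 0.5, r = 0.7 and two-sided alpha 5%. The standardized paired difference is 0.5/√(2 × (1 − 0.7)) = 0.5/√0.6 = 0.6455. The noncentral t gives 78.2% at n = 20 and 80.3% at n = 21, so the stated figure is reproduced to within two points. It concerns pre-post change in patients and does not involve controls. The plan gives no test or power for controls against IBS-D.

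**3. What control selection can and cannot bias.** For a single index, let P₀ and P₁ be the IBS-D means before and after LFD, H the mean in unexposed controls, and b the shift in the control mean caused by exposed controls. The two comparisons estimate (H + b) − P₀ and (H + b) − P₁. Subtracting the second from the first gives P₁ − P₀, and b cancels. So b biases each comparison with controls but not the pre-post change.

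**4. Size of b, as an illustration.** The group sizes (40 IBS-D, 30 controls) come from section 3.A and alpha from section 3.B. Two inputs are assumptions with no source in the documents: the share q of controls exposed (0.1-0.4, or 3 to 12 of 30) and the shift g in a diversity index (0.3-1.0 SD). Then b = q × g. With a two-sample t-test and no disease difference, the standard error is √(1/40 + 1/30) = 0.2415 SD, the noncentrality is b/0.2415, and there are 68 degrees of freedom.

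| q | g (SD) | b (SD) | Rejection rate at nominal 5% |
|---|---|---|---|
| 0.1 | 0.3 | 0.03 | 5.2% |
| 0.2 | 0.5 | 0.10 | 6.9% |
| 0.3 | 0.5 | 0.15 | 9.4% |
| 0.2 | 1.0 | 0.20 | 12.9% |
| 0.3 | 1.0 | 0.30 | 23.2% |
| 0.4 | 1.0 | 0.40 | 37.2% |

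The upper end, 0.40 SD, is close to the 0.5 that section 3.B calls a medium effect. The lower end is negligible.

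**5. Direction.** A control on an LFD moves the reference mean the way the diet moves patients. By the expressions in step 3, this brings the post-LFD mean closer to controls when the diet takes patients away from, or past, the healthy value. If the diet takes patients only part of the way toward healthy, the same shift widens the remaining gap. A falsely closer post-LFD result is therefore possible but not certain.

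**The case against.** The strongest reply is that unequal criteria are not in themselves a defect. Several IBS exclusions have plausible reasons that do not apply to someone who returns one stool sample: food allergy and diabetes for four weeks of supplied meals, pregnancy for sigmoidoscopy, antihistamines and mast-cell stabilizers for the mucosal mast-cell measurements. The protocol gives no rationale either way, so this is inference, but it is reasonable. The documents do not tie food allergy, pregnancy, antihistamines or mast-cell stabilizers to the stool microbiome. That part of the reply stands, and it is why restricted diet carries the point.

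A reader might infer that controls escape the surgery exclusion altogether. The documents do not support that: a known gastrointestinal history already bars a control, which would normally catch bowel surgery.

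A reader might also take any restricted diet in a control to make treated IBS-D look falsely healthy. For gluten-free or other restrictions the direction is unknown, and even for an LFD it depends on step 5. Nor would equal exclusions make diets uniform, since patients may receive vegetarian, vegan or omnivore meals.

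Finally, the comparison is ancillary. The listed aims concern the effect of LFD in IBS-D, and the power statement rests on paired tests. This limits the importance of the point but does not remove it, because the comparison is expressly planned and nothing later in the plan repairs it.

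**Conclusion.** The point holds for the comparison of control stool with IBS-D stool before and after LFD. Restricted diet, insulin-dependent diabetes and regular item vii drugs exclude patients but are neither excluded nor recorded in controls, so that comparison may be confounded. The exposure of most concern is the one the trial studies.

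The size is unknown. Under the assumed ranges the bias is 0.03-0.40 SD and the rejection rate about 5% to 37%, so it could be trivial or material. Those figures assume a two-sample t-test that the plan does not specify, all 40 and 30 subjects contributing, a common SD, and every exposure shifting the index in the same direction. Mixed exposures could offset one another. It would be tempting to quote a narrower figure, such as 13-23%, from shares of 20-30% and a full 1 SD shift. The documents give no basis for singling out that part of the range.

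Nor should a reader infer that the trial's main results are at risk: the within-patient pre-post analyses do not use the controls.

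**What to change.** In section 3.C, add to the healthy-volunteer exclusions at least the six-month restricted-diet criterion used for IBS patients. Preferably add insulin-dependent diabetes, cholecystectomy and the item vii drugs. Check these through the record review already planned in section 3.A, plus brief screening questions on diet and on regular medication, including over-the-counter products that records may miss.

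An acceptable alternative is to leave eligibility as it is, record diet, diabetes, cholecystectomy and regular medication in every control, and state in section 3.B that the comparison will be adjusted for them or repeated without exposed controls. With 30 controls, adjustment for several factors would be imprecise, so exclusion at enrolment is the simpler course for diet.

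The cost is a few eligibility lines, a short set of questions and slightly slower recruitment of 30 controls. No procedure is added.
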